6.4. UNSCHEDULED VISITS, RETESTS AND EARLY TERMINATION DATA

In general, for by-visit summaries, data recorded at the nominal visit will be presented. Unscheduled measurements will not be included in by-visit summaries if a nominal visit is performed in the same visit window but will contribute to the Last Observation Carried Forward (LOCF) value, and the worst-case value where required (e.g. overall post-baseline abnormal summaries).

In the case of a retest (same visit number assigned), the latest available measurement for that visit will be used for by-visit summaries.

Listings will include scheduled, unscheduled, retest and early termination data.

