6.5. DERIVED TIMEPOINT

An EOT timepoint will be derived and presented in the by-visit summaries. Data collected at the Week 24 visit or EOT visit will be pooled together under this EOT timepoint. This derived timepoint is for information purpose only and will not be included in any statistical models. That is, only descriptive statistics will be presented for this timepoint.

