6.6. WINDOWING CONVENTIONS

All assessments (scheduled, unscheduled, and early termination visits), excluding daily diary data (refer to Section 6.6.1), will be windowed as per [Table 1: Scheduled Visit Windows](#) to ensure all assessments fall into a scheduled visit in order to ensure all data are presented.

If more than one assessment is mapped to the same analysis visit, the following rules for selection of the assessment to use in the analysis will be applied:

- If a nominal and an unscheduled/early termination assessment are mapped to the same analysis visit, the nominal assessment will be selected over the unscheduled/early termination assessment. However, if the nominal assessment result is missing and the unscheduled or early termination assessment result is non-missing, the unscheduled/early termination assessment will be selected.
- In all other scenarios the visit closest to the target day will be selected. If two assessments were performed equally close to an analysis visit’s target day, one prior to and one after, the assessment before the analysis visit’s target day will be assigned to that analysis visit (except for the follow-up MRI assessment which is scheduled to be performed within 7 days after the Week 24/EOT visit).

Table 1: Scheduled Visit Windows

Assigned Visit	Target Day	Visit Windowing	
		Lower Limit	Upper Limit
Screening		-28	-1
Baseline ^a	1	-28	1
Week 2 ^b	15	2	22
Week 4 ^b	29	23	43
Week 8 ^b	57	44	71
Week 12 ^b	85	72	99
Week 16 ^b	113	100	127
Week 20 ^b	141	128	155
Week 24 ^b	169	156	183
4 weeks post-treatment ^c	28	14	42
8 weeks post-treatment ^c	56	43	70
12 weeks post-treatment ^c	84	71	98
16 weeks post-treatment ^c	112	99	126
20 weeks post-treatment ^c	140	127	154
24 weeks post-treatment ^c	168	155	182

^a See Section 6.3, the planned timepoint for Baseline is Day 1.

^b For Weeks 2 to 24, target day is calculated relative to the reference start date (refer to Section 6.1).

^c For post-treatment visits, target day is calculated relative to end of treatment date (refer to Section 6.2).

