15.2. SECONDARY EFFICACY

15.2.1. KEY SECONDARY EFFICACY ENDPOINTS AND DERIVATION

15.2.1.1. CFBL in CS7DA4S at Week 24

CFBL at Week 24 will be derived as described in Section 15.1.1.

15.2.1.2. Proportion of Subjects with at Least 1-point Decrease in Bilateral Zinreich Score in at Least One Pair of Anterior Ethmoid, Maxillary, Posterior Ethmoid, Frontal or Sphenoid Sinuses at Week 24

Sinus inflammation will be assessed by MRI at time points specified in the schedule of events in Section 8.1 of the protocol. The sinus inflammation will be assessed using the Zinreich modified Lund-Mackay scoring system (Likness, et al., 2014). The Zinreich score for each sinus will be assessed by Medical Metrics, Inc. (MMI) and all analysis will use the data collected by MMI. Six areas of each sinus (left and right) will be assessed:

- Anterior ethmoid
- Maxillary
- Posterior Ethmoid
- Frontal
- Sphenoid
- Ostiomeatal Complex (OMC)

Each area will be assigned a score based on the percentage of opacification as follows:

- 0=0%
- 1=1%-25%
- 2=26%-50%
- 3=51% to 75%
- 4=76% to 99%
- 5=100% or completely occluded

The OMC is given a score of 0 to 2 as follows:

- 0=completely patent
- 1=partially occluded
- 2=completely occluded

The bilateral Zinreich score for each area will be derived by [REDACTED] Biostatistics by adding the score for both sinuses together. The range of the score will be 0-10 except for OMC which will have a range of 0-4. The bilateral Zinreich score for each area will only be calculated if both sinus scores are non-missing. The total bilateral score

will be the sum of all 6 areas and will have a range of 0-54. The total bilateral score will only be calculated when all bilateral scores for each of the 6 areas are present. The baseline bilateral Zinreich score for each area and baseline total score will be the value recorded at screening. The individual and total Zinreich scores for all areas at all visits will be summarized and listed.

The key secondary endpoint will be the proportion of subjects with at least 1-point decrease from baseline in the Zinreich score in at least 1 pair of the anterior ethmoid, maxillary, posterior ethmoid, frontal or sphenoid sinuses at Week 24.

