15.2.3. MISSING DATA IMPUTATION METHODS FOR SECONDARY EFFICACY ENDPOINTS

15.2.3.1. Missing Data Imputation Methods for Key Secondary Efficacy Endpoints

For the primary analysis of the CFBL in CS7DA4S score at Week 24 key secondary efficacy endpoint, LOCF and multiple imputation will also be used to impute missing data for sensitivity analyses (refer to Section 15.1.4).

For bilateral Zinreich score and time-to-treatment failure, no imputation for missing data will be performed.

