15.2.4.2. Analysis of Zinreich Score

The number and percentage of subjects at Week 24 in the ITT analysis set with and without at least a 1-point decrease in one of the six bilateral Zinreich sinuses score as defined in Section 15.2.1.2 will be provided by treatment group.

A logistic regression adjusting for the baseline total bilateral Zinreich score and stratification variables (nasal allergy and nasal polyps) will be used to compare treatment groups. The responder indicator will be set to 1 for subjects who achieve at least a 1-point decrease in any score at Week 24 compared to baseline. Subjects for whom the decrease cannot be calculated, for example due to early termination, will be excluded from the analysis.

Odds ratios together with the 90% CI will be presented to compare treatment groups. This analysis will be repeated for the PP analysis set.

As non-key secondary analyses, the CFBL in each of the 5 bilateral Zinreich sinuses score, Zinreich OMC score and total Zinreich score at Week 24 will be analyzed using an ANCOVA model as specified in Section 15.1.3 replacing the baseline CS7DA4S with the appropriate baseline bilateral Zinreich sinuses score, Zinreich OMC score or baseline Zinreich total score. This analysis will be repeated for the PP analysis set.

Additionally, the logistic regression and ANCOVA models will be repeated on the subgroups as per baseline median total bilateral Zinreich score, for the ITT analysis set.

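### As written, the SAP's visit windows omit follow-up MRIs that the protocol plans from the key secondary Zinreich analysis: pre-rescue and early-termination scans before Day 156, and scans deferred from an on-time Week 24 visit

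*SAP*

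**What the plan says.** Protocol:

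- Section 8.3.2, with footnote q to Table 1 in 8.1, plans one follow-up MRI per subject, normally within 7 days of the removal procedure at Week 24/EOT. There are two exceptions. If oral-corticosteroid rescue is needed during treatment, the scan is done before rescue and replaces the Week 24/EOT scan. If the subject has, or is recovering from, a cold, an allergy exacerbation or a respiratory infection at EOT, the scan waits until 4 weeks after that event resolves.
- Section 4.1.2 requires the EOT assessments at an early-termination (ET) visit, which by implication includes the MRI.
- Section 10.6.2.2 analyses ITT subjects who have a post-treatment MRI and sets no study-day window. Sections 3 and 10.6.2 label the endpoint as a Week 24 endpoint.

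SAP:

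- Section 6.6: "All assessments (scheduled, unscheduled, and early termination visits), excluding daily diary data" are placed in visits by Table 1, where Week 24 is Days 156-183. The only MRI wording belongs to the rule for two assessments equally close to a target day: "except for the follow-up MRI assessment which is scheduled to be performed within 7 days after the Week 24/EOT visit".
- Section 6.5 pools Week 24 and EOT data into one timepoint, but "This derived timepoint is for information purpose only and will not be included in any statistical models".
- Section 15.2.4.2: the "responder indicator will be set to 1 for subjects who achieve at least a 1-point decrease in any score at Week 24", and "Subjects for whom the decrease cannot be calculated, for example due to early termination, will be excluded from the analysis".
- Section 15.2.3.1: "For bilateral Zinreich score and time-to-treatment failure, no imputation for missing data will be performed".
- Section 15.2.1.2 refers MRI timing to protocol 8.1 and adds: "The individual and total Zinreich scores for all areas at all visits will be summarized and listed".
- Section 6.4: "In general, for by-visit summaries, data recorded at the nominal visit will be presented".
- Section 3.3, the list of changes from the protocol, does not mention this point.

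**The concern.** The protocol arranges a scan for subjects who are rescued, stop early or are ill at EOT, so that they still have an imaging outcome. The SAP's general windowing rule then appears to place many of those scans in visits that the Zinreich model never uses. A pre-rescue scan replaces the Week 24 scan, so no second scan is planned for that subject, and the subject leaves a key secondary analysis although the outcome was observed.

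Some of this loss is related to outcome. A physician's recommendation of oral corticosteroid or ESS for worsening CS is itself treatment failure (protocol 10.6.2.3), and needing ESS is a listed reason for stopping treatment (protocol 4.3). Other losses are not of this kind: protocol 6.4.4 also allows oral corticosteroid for an asthma flare-up, and a deferral follows an intercurrent illness.

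**Working it through.** **The window.** Week 24 target = 24 × 7 + 1 = Day 169. The lower limit is the day after the midpoint of the Week 20 and Week 24 targets: (141 + 169)/2 = 155, so Day 156. The upper limit is 169 + 14 = Day 183. This reproduces SAP Table 1.

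**Scan at an on-time visit, not deferred.** The visit is due on Day 169 ± 3, i.e. Days 166-172. With up to 7 days for the MRI, the scan falls on Days 166-179, inside the window.

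**Pre-rescue scan.** By study day, a scan on Day 90 maps to Week 12 and one on Day 155 to Week 20. From Day 156 it maps to Week 24. Every pre-rescue scan before Day 156 is therefore outside.

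**ET scan, not deferred.** A scan before Day 156 maps to an earlier week. If the 7-day allowance also applies at ET, a visit up to Day 148 gives a scan no later than 148 + 7 = Day 155, always outside. Visits on Days 149-155 can go either way.

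**Scan deferred from an on-time visit, illness still present then** (4 weeks = 28 days):

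| Visit | Earliest scan | Days past Day 183 |
|---|---|---|
| Day 166 | 166 + 28 = Day 194 | 11 |
| Day 169 | 169 + 28 = Day 197 | 14 |
| Day 172 | 172 + 28 = Day 200 | 17 |

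Counted from the EOT visit, such a scan is on post-treatment Day 28 or later, in the 4-week post-treatment window (Days 14-42) or a later one. To fall by Day 183, the illness must have resolved by 183 − 28 = Day 155, which is 11 to 17 days before the visit.

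**Scan deferred after ET.** It falls on Days 156-183 if the illness resolves on Days 128-155 (156 − 28 to 183 − 28). Example: ET on Day 100, resolution on Day 135, scan on Day 163. That is Week 24 by study day, but also post-treatment Day 163 − 100 = 63, in the 8-week window (Days 43-70). Table 1 gives no precedence.

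**Is there another way into the model?**

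- The pooled EOT timepoint is descriptive only (6.5).
- There is no imputation for the key secondary score (15.2.3.1). SAP 15.2.3.2 limits LOCF to CS7DA4S and SNOT-22 endpoints.
- SAP 15.3.1.4 lists no Zinreich analysis at post-treatment visits, and SAP 4.3 lists no MRI in the final analysis.

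The same holds for the Zinreich change-from-baseline ANCOVAs, which 15.2.4.2 also ties to Week 24.

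**Illustration of size.** The documents give no rate for rescue, ET or deferral. Assume 21 evaluable per arm (the Week 4 figure in SAP 7.1) and 10 responders, 10/21 = 47.6%:

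- One non-responder omitted: 10/20 = 50.0%, up 2.4 points.
- One responder omitted: 9/20 = 45.0%, down 2.6 points.
- Extremes: 20/21 = 95.2% becomes 20/20 = 100%, and 1/21 = 4.8% becomes 0/20 = 0%, each a shift of 4.8 points.

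**The case against.** The best counter-argument is that the authors meant these scans to count. SAP 15.2.1.2, which defines the endpoint, sends MRI timing to protocol 8.1, and footnote q there ties the pre-rescue and deferred scans to the EOT MRI. SAP 6.4 speaks of nominal visits, the stated aim of 6.6 is to get all data presented, and the vendor's visit labels are not visible to us. This stands as evidence of intent and of real ambiguity. It does not supply a rule: nothing in the SAP maps these scans to Week 24. SAP 6.4 concerns by-visit summaries, and 6.6 windows scheduled visits by date as well.

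A reader might infer that the exclusion sentence in 15.2.4.2 by itself discards ET scans. It does not, because it also fits a subject who has no follow-up MRI. The omission comes from reading it with 6.5 and 6.6.

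A reader might also infer a plain contradiction of the protocol. That goes too far. The protocol labels the endpoint as Week 24, and post-treatment in 10.6.2.2 does not literally describe a scan taken before rescue with depots in place. Whether the SAP departs from the protocol is therefore unclear for pre-rescue scans.

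Finally, restricting the analysis to scans near Week 24 is a defensible choice of estimand. That stands too, provided the choice is stated.

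**Conclusion.** The point holds as a reading of the SAP's rules taken together. Pre-rescue and ET scans before Day 156, and scans deferred from an on-time Week 24 visit for illness still present then, do not enter the Zinreich logistic regression or ANCOVAs. Scans from Day 156 to Day 183 stay in, subject to the unresolved overlap after ET. The omitted scans would still be listed and summarized descriptively.

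The number of subjects affected and the direction of any bias cannot be derived, so the documents do not support a claim that the omission favours LYR-210 or sham. Nor does each omitted scan shift the responder rate by 4.8 points: 1/21 is one subject's weight, and a shift of that size arises only at the extremes. At 10/21 the shift is 2.4 or 2.6 points, on the assumption of 21 evaluable per arm at Week 24.

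The consequence is limited. SAP 7.8 calls the study exploratory and reports nominal p-values, and the Week 4 primary analysis is untouched. The rule still deserves correction, because it drops observed and partly outcome-related data from a key secondary analysis, and two programmers could build different analysis sets from it. Confidence is medium because of the ambiguity in 6.4 and 15.2.1.2.

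**What to change.** - In SAP 6.6 and 15.2.4.2, state that each subject's protocol-designated follow-up MRI (Week 24/EOT, ET, pre-rescue or deferred) is assigned to the Week 24/EOT Zinreich analysis whatever its study day, for both the logistic regression and the ANCOVAs.
- Report the analysis restricted to Days 156-183 beside it.
- If the sponsor prefers the restricted set as the main analysis for estimand reasons, report the all-follow-up-MRI analysis as the sensitivity analysis, and note the restriction against protocol 10.6.2.2 in SAP 3.3.
- Add a rule for deferred scans that fall after the primary-analysis cut-off, since SAP 4.2 excludes data collected after that date.
- Optional: an analysis that counts subjects rescued or terminated early for worsening CS as non-responders.

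The cost is SAP wording and one or two extra tables, with no new data. The downside is that the pooled set mixes exposure durations, with some scans well before Week 24 and some four or more weeks after removal. If rescue differs by arm, the arms are compared at different exposures, which is why both versions should be shown.

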15.2.4.3. Analysis of Time-to-Treatment Failure

The number and percentage of subjects with and without treatment failure will be presented based on the ITT analysis set. For subjects without treatment failure, the censoring reason will be summarized. Time-to-treatment failure (days) will be analyzed for the ITT analysis set using a Cox proportional hazards model with fixed effects for baseline CS7DA4S score, treatment group and the stratification variables (nasal allergy and nasal polyps). The Hazard ratio of each LYR-210 treatment group vs. the Sham treatment group, its 90% CI and p-values will be presented.

Additionally, Kaplan-Meier results will be displayed for the 25%, 50% and 75% quartiles, along with Kaplan-Meier estimates of probability of treatment failure at different timepoints: Weeks 2, 4, 8, 12, 16, 20 and 24. These timepoints are independent of the scheduled visits. Kaplan-Meier plots of time-to-treatment failure will be produced for each treatment group.

15.2.4.4. Analysis of Time-to-Onset of Action

Each daily CFBL in CS7DA4S values will be summarized and analyzed as the primary efficacy endpoint (see to Section 15.1.3).

The daily LS mean CFBL (+/- SE) in CS7DA4S up to Day 30 will be presented graphically for each treatment group in the ITT analysis set with an indicator as to when the LYR-210 treatment groups are statistically significantly greater than the Sham group.

For each LYR-210 group, the time-to-onset action will be the earliest day at which statistical significance is reached in comparison with the Sham group, when statistical significance is also reached for all subsequent visits. For example, if Days 10, 13, 14 and all subsequent days reached statistical significance for a LYR-210 group against the Sham group, time-to-onset of action will be Day 13 even if statistical significance was reached at Day 10 because statistical significance was not reached at Days 11 and 12.

15.2.4.5. Analysis of SNOT-22 and SF-36v2 Domain and Total Scores

For each post-Day 1 visit, the questionnaires will be compared between treatments using an ANCOVA model as described for the primary endpoint in Section 15.1.3 for the ITT analysis set. The CS7DA4S baseline score in

Section 15.1.3 will be replaced by the baseline score for the domain/total score of interest in the ANCOVA model. The summary of SNOT-22 will include the proportion of subjects who have achieved a minimally clinically important difference.

Additionally, a plot of the biweekly LS means and SE for CFBL for SNOT-22 total score over time up to Week 24 and Week 48 by treatment group will be provided for the primary and final data analyses, respectively.

The analysis for SNOT-22 will be repeated for the PP analysis set. In addition, analysis for SNOT-22 in the ITT analysis set will be repeated where missing data will be imputed using the LOCF method outlined in Section 15.1.4.

15.2.4.6. Analysis of UPSIT™

The UPSIT™ score at Week 24 will be analyzed for the ITT analysis set using an ANCOVA model outlined in Section 15.1.3. The Baseline CS7DA4S score will be replaced by the baseline UPSIT™ score in the model.

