7.7. STATISTICAL TESTS

The default significance level will be 5% and all tests will be one-sided, unless otherwise specified in the description of the analyses. Two-sided 90% CIs will be presented for all outputs were relevant.

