7.8. MULTIPLE COMPARISONS/MULTIPLICITY

The primary objective of this study is to test the following null and alternative hypotheses:

$$H_0: \mu_{L_{2500}} = \mu_C \text{ vs. } H_1: \mu_{L_{2500}} < \mu_C$$

$$H_0: \mu_{L_{7500}} = \mu_C \text{ vs. } H_1: \mu_{L_{7500}} < \mu_C$$

where $\mu_{L_{2500}}$, $\mu_{L_{7500}}$ and μ_C are the true mean values of the CFBL in the CS7DA4S score at Week 4 for the LYR-210 2500 μg , LYR-210 7500 μg , and control (Sham procedure) treatment groups, respectively.

Given the exploratory nature of the study, no adjustment to the overall alpha-level of the study will be made for multiple comparisons and multiplicity. That is, only nominal p-values will be provided for the primary efficacy endpoint, key secondary endpoints, non-key secondary endpoints, and exploratory efficacy endpoints.

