15.1.3. PRIMARY ANALYSIS OF PRIMARY EFFICACY ENDPOINT

The CFBL for CS7DA4S at Week 4 will be analyzed using the ITT analysis set. The following analysis will be performed for the CFBL CS7DA4S score at Week 4:

- Summary statistics for the Baseline CS7DA4S score, the Week 4 CS7DA4S score and the CFBL at Week 4
- An ANCOVA model for CFBL at Week 4. The ANCOVA model will include the baseline CS7DA4S score as a covariate, treatment group and the randomization stratification variables (nasal allergy, nasal polyps) as fixed effects.

Each hypothesis as described in Section 7.8 will be tested at a one sided 0.05 alpha level of significance by the ANCOVA model. The LS means and SE of each treatment group, the LS mean difference of each LYR-210 procedure against the Sham procedure and their SEs, 90% CIs, and p-values estimated by the model will also be provided.

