Rhinologic Symptoms	#1, #2, #3, #4, #7, #12	0–30
Extra-Nasal Rhinologic Symptoms	#5, #6, #7	0–15
Ear/Facial Symptoms	#3, #8, #9, #10, #11	0–25
Psychological Dysfunction	#16, #17, #18, #19, #20, #21, #22	0–35
Sleep Dysfunction	#13, #14, #15, #16, #17	0–25

The total SNOT-22 score will also be calculated as the sum of all 22 questions and will have a range of 0-110. For the total score, if less than 50% of the items are missing at a visit for a subject, the missing items will be imputed with the mean of the subject’s non-missing items at that visit prior to the total score calculation. Otherwise if 50% or more of the questionnaire items are missing at a visit for a subject, the total score will be set to missing at that visit for that subject.

CFBL in the total and subdomain SNOT-22 scores will be derived for Weeks 2, 4, 8, 12, 16, 20 and 24 as per Section 6.7. If a subject’s CFBL in total SNOT-22 score is greater than 8.9 (i.e. the score decreased by more than 8.9), the subject is considered to have achieved a minimally important clinical difference.

15.2.2.4. Change from Baseline in Bilateral Zinreich Anterior Ethmoid, Maxillary, Posterior Ethmoid, Frontal, Sphenoid and OMC Sinus Scores, and Total Score at Week 24

The bilateral Zinreich anterior ethmoid, maxillary, posterior ethmoid, frontal, and sphenoid scores at Week 24 will be calculated as defined in Section 15.2.1.2. The bilateral Zinreich OMC and total Zinreich scores will also be calculated as defined in Section 15.2.1.2.

Then, the CFBL in each of these endpoints will be calculated at Week 24 as per Section 6.7.

15.2.2.5. 36-Item Short Form Health Survey Version 2 (SF-36v2) Questionnaire

The SF-36v2 questionnaire is a multi-purpose, short-form health survey with 36 questions/items. It yields 8 functional health and well-being domains as well as 2 psychometrically-based physical and mental overall component summary measures, where lower scores imply higher disability (i.e., a score of zero is equivalent to maximum disability and a score of 100 is equivalent to no disability).

The 8 domains of the SF-36 are (refer to Table 4: SF-36v2® Health Survey Measurement Model):

- Physical Functioning (PF)
- Role-Physical (RP)
- Bodily Pain (BP)
- General Health (GH)

- Vitality (VT)
- Social Functioning (SF)
- Role-Emotional (RE)
- Mental Health (MH)

The two overall component summary measures are (refer to [Table 4: SF-36v2® Health Survey Measurement Model](#)):

- Physical Component Summary (PCS)

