15.2.2.6. University of Pennsylvania Smell Identification Test (UPSIT™)

The UPSIT™ is composed of 40 odorants embedded on scent strips that are released when scratched with a sharply tipped object (Doty, Shaman, & Dann, 1984). The UPSIT™ is comprised of 4 booklets, each containing 10 microencapsulated (scratch & sniff) odours. The UPSIT™ is a forced-choice test, and subjects will be instructed to identify each odorant with alternatives accompanying each test item. The total olfaction score using the UPSIT™ is defined as the number of odorants correctly identified out of the 40 odours tested, with higher scores designating better olfactory performance.

The total olfaction score will be collected on the UPSIT eCRF page. The change from baseline in UPSIT™ total score will be calculated at each post-baseline visit as per Section 6.7.

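### The SAP sends UPSIT and SF-36v2, where higher is better, to a one-sided analysis whose only stated alternative is lower-than-sham, and its SNOT-22 responder inequality has the wrong sign

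*SAP*

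**What the plan says.** **Sidedness.** SAP 7.7: "The default significance level will be 5% and all tests will be one-sided", unless a section specifies otherwise. It names no direction. The protocol synopsis and Protocol 10.6.2 also set a one-sided 0.05 level for secondary endpoints without naming one.

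**Alternative.** SAP 7.8 writes one pair of hypotheses, one per dose, each with the LYR-210 mean below the sham mean. The means "are the true mean values of the CFBL in the CS7DA4S score at Week 4".

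**Primary test.** SAP 15.1.3 sets out the ANCOVA and adds: "Each hypothesis as described in Section 7.8 will be tested at a one sided 0.05 alpha level of significance".

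**Reuse.** For SNOT-22 and SF-36v2, SAP 15.2.4.5 says "the questionnaires will be compared between treatments using an ANCOVA model as described for the primary endpoint in Section 15.1.3". UPSIT (SAP 15.2.4.6) "will be analyzed for the ITT analysis set using an ANCOVA model outlined in Section 15.1.3". Each section names one substitution, the baseline score. SAP 15.3.3 compares continuous exploratory endpoints in the same manner as the primary efficacy analysis. Protocol 10.6.3 likewise refers continuous non-key secondary endpoints to the primary endpoint's method.

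**Scale direction.** UPSIT is scored "with higher scores designating better olfactory performance" (SAP 15.2.2.6). SAP 15.2.2.5 says that lower SF-36v2 scores mean more disability. On SNOT-22 and CS7DA4S, higher is worse.

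**SNOT-22 responder.** SAP 6.7 defines change from baseline as the visit value minus the baseline value. SAP 15.2.2.3 counts a subject as having reached the minimally important difference if "CFBL in total SNOT-22 score is greater than 8.9", and explains in a parenthesis that the score fell by more than 8.9.

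**The concern.** A one-sided test needs a stated tail. The SAP states one tail, for a scale on which improvement is a negative change, and then routes two instruments on which improvement is a positive change through the same section. The authors did adapt Section 15.1.3 for these instruments, since they swapped the covariate, but they did not adapt the direction.

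A programmer who applies 15.1.3 as it stands would report p-values near 1 for a real benefit on smell identification or general quality of life, and small p-values for a real worsening. A programmer who notices the problem has to choose the tail without written authority. If that choice is made after unblinding, it is open to criticism.

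The SNOT-22 rule is a smaller instance of the same sign problem. It feeds the proportion of subjects with a minimally clinically important difference, which SAP 15.2.4.5 requires in the SNOT-22 summary.

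**Working it through.** **1. The plan's own figure.** SAP 7.1 gives means of −1.30 (sham) and −3.00 (LYR-210), SD 2.4, 21 evaluable subjects per group, one-sided 0.05 and 73% power.
- Standard error of the difference = 2.4 × √(2/21) = 0.741.
- Noncentrality = 1.70 / 0.741 = 2.295.
- Noncentral t, one-sided 0.05: 73.0% with 40 df (two arms) and 73.4% with 60 df (three arms pooled). The two-sided versions give 61–62%.

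The 73% therefore reproduces as a one-sided test of one dose against sham, with benefit as a larger fall. The primary test is in the correct tail.

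**2. Direction by endpoint.** Change is visit minus baseline throughout (SAP 6.7).

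| Endpoint | Better score | Change under benefit | Alternative reached through 15.1.3 | Match? |
|---|---|---|---|---|
| CS7DA4S, Weeks 4 and 24 | lower | negative | LYR-210 < sham | yes |
| SNOT-22 total and domains | lower | negative | LYR-210 < sham | yes |
| Zinreich change scores | lower | negative | LYR-210 < sham | yes |
| UPSIT | higher | positive | LYR-210 < sham | no |
| SF-36v2 domains, PCS, MCS | higher | positive | LYR-210 < sham | no |

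**3. Effect on the p-value.** The ANCOVA has six parameters (intercept, two treatment terms, baseline, allergy, polyps), so 63 evaluable subjects leave 63 − 6 = 57 df. Take an illustrative t = 2.0 in favour of LYR-210 on UPSIT.
- Intended upper tail: P(T > 2.0) = 0.025.
- Literal lower tail: P(T < 2.0) = 0.975 = 1 − 0.025.
- Two-sided 90% interval in standard-error units: 2.0 ± 1.672, lower limit 2.0 − 1.672 = 0.328. It excludes zero in favour of LYR-210.

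The output would then pair p = 0.975 with an interval wholly on the side of benefit. The estimate, its standard error and the interval do not depend on the tail.

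**4. Number of outputs.** At Week 24: 1 UPSIT + 8 domains + 2 summaries = 11 scores, × 2 doses = 22 one-sided p-values. The polyp-subgroup repeats (SAP 15.3.1.3), UPSIT at Week 28 and SF-36v2 at Week 48 (SAP 15.3.1.4) follow the same rule through 15.3.3.

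**5. SNOT-22 responder rule.**

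| Baseline → visit | CFBL | CFBL > 8.9 | Fell by more than 8.9 |
|---|---|---|---|
| 50 → 30 | −20 | no | yes |
| 50 → 45 | −5 | no | no |
| 50 → 60 | +10 | yes | no |

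No subject can satisfy both halves of the sentence. The inequality picks out subjects who worsened; the parenthesis picks out those who improved.

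**The case against.** **The cross-reference imports a model, not a hypothesis.** SAP 7.8 confines its alternative to CS7DA4S at Week 4, and 15.2.4.5 and 15.2.4.6 cite the ANCOVA model. On this reading the direction for UPSIT and SF-36v2 is unstated rather than wrong. This stands in part, and is why the conclusion is conditional on a word-for-word reading. It does not clear the text. Section 15.1.3 includes the test as well as the model, and Protocol 10.6.3 and SAP 15.3.3 carry over the manner of comparison as a whole. Even on the kinder reading, a one-sided test without a stated tail is not fully specified.

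**The intended direction is obvious.** The objectives in SAP 2.3 speak of improving quality of life and smell function, and the scale directions are given. This stands as evidence of intent, but it is not a stated alternative.

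**The SNOT-22 sentence corrects itself.** It does. SAP 15.2.2.1 and 15.2.4.4 also use "greater" for a larger improvement in CS7DA4S, which supports reading the word as size of improvement. A reader might infer that subjects who worsened will be counted as responders; that would require the programmer to ignore the parenthesis.

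**Little hangs on it.** The endpoints are non-key secondary or exploratory, SAP 7.8 provides nominal p-values only, and the estimates and intervals would expose the error. All of this stands. The table shells that accompany the SAP are not available here, so what would actually be printed cannot be settled.

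**Conclusion.** The text is wrong as written, within narrow limits. If Section 15.1.3 is followed word for word, the one-sided p-values for UPSIT and all ten SF-36v2 scores become 1 minus the intended values: 22 at Week 24, plus the exploratory repeats. The SNOT-22 responder inequality contradicts its own parenthesis under SAP 6.7; the intent is clear and only the sign needs correcting.

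Not affected: the primary endpoint, the key secondary CS7DA4S analysis at Week 24, the SNOT-22 ANCOVA, and every least-squares mean difference and 90% confidence interval.

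Two stronger readings should be resisted. One is that the trial will test these endpoints for harm. The documents do not establish that, because Section 7.8 is worded for CS7DA4S and the objectives point the other way. The other is a loss-of-power figure for UPSIT or SF-36v2. The documents give no effect size for either, and borrowing the primary endpoint's would be arbitrary. The t = 2.0 example is illustrative only.

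**What to change.** In SAP 7.7 or 7.8, state the one-sided alternative by endpoint:
- UPSIT and all SF-36v2 domain, PCS and MCS scores: μ_LYR > μ_C.
- Change from baseline in symptom, SNOT-22 and Zinreich scores: μ_LYR < μ_C.
- For completeness, since the SAP names no direction for them either: odds ratio > 1 for the Zinreich responder endpoint and hazard ratio < 1 for treatment failure, each LYR-210 against sham.

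In SAP 15.2.2.3, write the responder rule as CFBL < −8.9 and drop the parenthesis.

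The cost is a few sentences and a check that the table shells and programs agree. No data, model or sample size changes. The change should be dated before unblinding so that the choice of tail cannot be questioned later.
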